1.0 OBJECTIVES

Primary Objective

To estimate the efficacy of PT2385 as measured by radiographic response rate (by Response Assessment in Neuro-Oncology, RANO, criteria) in patients with recurrent glioblastoma

Secondary Objectives

1. To estimate the efficacy of PT2385 as measured by progression free and overall survival in patients with recurrent glioblastoma
2. To determine the safety of oral PT2385 in patients with recurrent glioblastoma

Exploratory Objectives

1. To describe the pharmacokinetic and pharmacodynamic properties of PT2385 in patients with recurrent glioblastoma
2. To describe baseline intratumoral hypoxia using novel, advanced MR-based neuroimaging sequences in patients with recurrent glioblastoma
3. To explore genetic polymorphisms involved in the metabolism of PT2385

2.0 BACKGROUND AND RATIONALE

2.1 Glioblastoma

Although the recent addition of temozolomide (TMZ) to radiation therapy for the treatment of glioblastoma (GBM) has resulted in improved outcomes, the estimated 2year survival with maximal therapy remains only 27% (Stupp, et al., 2005; Stupp, et al., 2009). Almost all GBMs progress, with a median time to progression of approximately 7 months. The prognosis is very poor for patients who have progressive/recurrent GBM. There is currently no standard therapy for recurrence. Salvage chemotherapies are largely ineffective, with progression-free survival at 6 months (PFS6) rates of 10-15%. Bevacizumab therapy at recurrence is associated with a high response rate, but not

significantly increased survival. Survival after failure of bevacizumab administered for GBM recurrence is very poor with a median survival of 4-6 months and PFS 6 of 0 (Reardon, et al., 2012). Hence, new therapies for recurrent GBM are urgently needed.

Hypoxia is a prominent feature of the tumor microenvironment in GBM. Pseudopallisading necrosis, one of the defining histologic characteristics of GBM, represents hypoxic tumor cells migrating away from dysfunctional vasculature (Rong, Durden, Van Meir, & Brat, 2006). This hypoxic environment promotes the self-renewal properties of glioma stem cells (GSCs) and may even drive non-stem cells toward a stemlike phenotype (Heddleston, Li, Hjelmeland, & Rich, 2009). Furthermore, hypoxia has been implicated as a potential mechanism of resistance to radiation therapy, a critical aspect of GBM treatment. However, to date few therapeutic agents have been developed which successfully modulate hypoxia pathways and improve outcomes in GBM.

2.2 PT2385

Rationale for the Therapeutic Target and Pathway

Several biochemical pathways mediate the cellular effects of hypoxia. Most importantly are the roles of the hypoxia inducible factors (HIFs). While HIF1-alpha (HIF1a) has been perhaps most widely studied in a variety of cancer models, HIF2a is potentially a more appealing target in GBM. HIF2a drives expression of numerous genes involved in angiogenesis (i.e. VEGFA), proliferation (i.e. cyclin D1), cell survival (e.g. class III betatubulin), and immune evasion (i.e. CD73). In contrast to HIF1a which is expressed in both GSCs and normal neural progenitors, HIF2a is specific and selective for GSCs (Li et al., 2009). In fact, the effects of hypoxia on the GSC phenotype has been shown to be directly mediated by HIF2a (Seidel et al., 2010). Dual labeling immunofluorescence studies show that HIF2a is co-expressed in cells expressing stem-cell markers (i.e. CD133) in perivascular locations and around areas of necrosis (Li et al., 2009). Furthermore, HIF2a and not HIF1a has been shown to regulate genes involved in mediating hypoxia-induced stemness (i.e. MAML3, NFATc2), promoting CD133 expression, and increasing neurosphere formation (Seidel et al., 2010). HIF2a is associated with CDH5-mediated neovasclogenesis in stem cell populations (Mao, Xue, Wang, Zhang, & Yan, 2013). HIF2a has been linked to over-expression of class III beta-tubulin, a survival factor that rescues cells from programmed cell death and has been linked to chemoresistance (Bordji, Grandval, Cuhna-Alves, Lechapt-Zalcman, & Bernaudin, 2014), aggressiveness (Katsetos, Dráberová, Legido, Dumontet, & Dráber, 2009), and poor prognosis (Ferrandina et al., 2006; Zhang et al., 2012). In conclusion, targeting HIF2a represents an opportunity to focus on a fundamental component of GBM (e.g. hypoxia) and potentially target the stem-like cell population which is purported to contribute to glioma heterogeneity, resistance to current therapies, and disease recurrence.

Preclinical Data in GBM

PT2399, a close structural analog of PT2385 with comparable brain uptake and the tool molecule used by external collaborators for preclinical testing, was evaluated in 4 orthotopic patient-derived xenograft (PDX) models of GBM. Survival benefit was observed in 3 of 4 models tested (Table 1, Figure 1a & 1b) with an average survival advantage ranging 12-45% (all $p < 0.001$). Growth inhibition has also been observed in an orthotopic renal cell carcinoma brain metastasis model (personal correspondence: [name] and [name], University of Texas at Southwestern Medical Center).

[figure not shown]

Figure 2: Rat brain & plasma PK after 3 days dosing of PT2385 (100 mg/kg)

Blood Brain Barrier Penetration

An important component of the development of novel drugs for treatment of GBM is the ability to cross the blood brain barrier (BBB). PT2385 has favorable characteristics for blood brain penetration in humans including low molecular weight (383 Da), low water solubility (log D value in octanol/water pH 7.4 is 2.19; < 3 being favorable), and high brain/plasma ratio in rats (ratio 0.9, Fig 2).

Studies in animals demonstrated the oral bioavailability to be 40% in rats and ~90% in dogs. The volume of distribution is greater than the total body water in mice, rats, dogs, and monkeys with a t_{max} between 0.5-2 hours and terminal half-life of 9 and 12 hours in rat plasma and brain, respectively. Plasma protein binding of PT2385 was 82% for human plasma protein with half-life of approximately 14 hours. The drug undergoes oxidative metabolism via CYP2C19 and CYP3A4 and O-glucuronidation (UDP-glucuronosyltransferase-2B7 isoenzyme) to form an inactive glucuronide conjugate (PT2639). PT2385 induced concentration-dependent increases in CYP2B6 and CYP3A4 mRNA cultured human hepatocytes with half-maximal effective concentrations (EC_{50} values) ranging from 10.3 to 33.5 μM (4-13 $\mu\text{g/mL}$) for CYP2B6 and from 9.3-41.2 μM (3.616 $\mu\text{g/mL}$) for CYP3A4.

Prior and Ongoing Clinical Trials with PT2385

As of August 15, 2016, PT2385 had been studied in 70 subjects, 16 healthy volunteers and 54 patients with ccRCC. Fifty-one patients have been enrolled in Part 1 of Study PT2385-101, the first-in-human study of PT2385; 26 patients were enrolled in the dose-escalation portion of Part 1, which has now completed enrollment and all dose-limiting toxicity evaluation periods. The dosages evaluated in the dose-escalation portion ranged from 100 to 1800 mg b.i.d. No dose-limiting toxicities were observed; no patients died during the study and no patients were discontinued from the study because of adverse events (AEs). The 800 mg b.i.d. dosage was selected as the recommended phase

2 dose based on an assessment of safety, pharmacokinetic, and pharmacodynamic data (Courtney et al., 2016). Twenty-five patients were enrolled in the dose expansion portion of Part 1 at a dosage of 800 mg b.i.d.

The most commonly reported AEs among the 51 patients enrolled in Part 1 were anemia, fatigue, peripheral edema, nausea and lymphocyte count decreased. Most AEs have been mild to moderate in severity and were reported as National Cancer Institute (NCI) Common Terminology Criteria for Adverse Events (CTCAE) Grade 1 to 2. The most common Grade 3/4 toxicities included anemia (5), decreased lymphocyte counts (5), hypoxia (5), and hypophosphatemia (3). One patient had a complete response (CR), four patients had a partial response (PR), and 17 patients had stable disease for more than 16 weeks. The longest duration of treatment has been 537 days for a patient in the 200 mg b.i.d. dosage group and 468 days for a patient treated at the 800 mg b.i.d dose.

In Part 2 of the study, PT2385 (800 mg b.i.d. orally) is being evaluated in combination with nivolumab (Opdivo®) (3 mg/kg intravenously once every two weeks). Three patients with ccRCC have been treated with the combination of PT2385 and nivolumab. There were 10 reported AE's; photophobia was the only event reported in more than one patient (2). All AE's in Part 2 were reported as Grade 1, with the exception of one Grade 3 AE of pleural effusion, which also met SAE criteria. The event of pleural effusion was considered not related to PT2385, but related to progressive disease.

Study PT2385-102 evaluated the effect of food on the pharmacokinetics of PT2385 in 16 healthy female volunteers in a crossover study. The presence of food had a mild effect (19% to 37% increase) on the exposure to PT2385 in this study; little to no effect was observed in exposure to PT2639 (the primary metabolite of PT2385) in the presence of food. The most common adverse events were headache, venipuncture site bruising, and nausea.

2.3 Rationale

Based on preclinical efficacy as a single-agent, favorable blood brain barrier penetrating properties, and acceptable safety profile with an established recommended phase II dose, we propose a phase II efficacy study of PT2385 in recurrent GBM. This study will provide the first-ever experience of PT2385 in GBM and provide the initial clinical experience of targeting this novel therapeutic pathway.

Bevacizumab-naïve patients have been specifically selected for this study. PT2385 is unlike other agents currently approved for the treatment of recurrent GBM. Though PT2385 potentially inhibits tumor production of VEGF, its action is well upstream of VEGF with widespread cellular action on cyclin D1, CD73, GLUT1, and others. Clinically, VEGF tyrosine kinase inhibitors are associated with hypertension; however, such findings could not be recapitulated in preclinical models of PT2385 treated rats (Fig 3). To avoid any potential impact of bevacizumab on tumor associated hypoxia, in this first experience of PT2385 in GBM, we propose to study this agent in bevacizumab-naïve patients at first recurrence.

[figure not shown]

Figure 3: HIF-2 α Antagonism does NOT recapitulate anti-angiogenic effects in rats

Radiographic response has been specifically selected as the primary endpoint in this study and is supported by recent Cancer Treatment and Evaluation Program (CTEP)-approved trials ongoing within the Adult Brain Tumor Consortium (ABTC) including ABTC 1402. Overall and progression-free survival data will be gathered as secondary endpoints to inform subsequent drug development in this population.

Overall, this study will provide an initial experience of the clinical activity of PT2385 in GBM as a single agent. If positive, subsequent studies will determine the safe and effective dose of PT2385 which can be combined with radiation and/or temozolomide as a new therapeutic approach in the newly diagnosed setting.

In a condition with a dismal prognosis and limited therapeutic options, PT2385 is an extremely attractive agent for study. It targets a signaling pathway that is highly relevant for GBM and for which no similar agents are currently undergoing testing. Pharmacologic properties (i.e. molecular weight <400 Da, low water solubility) support ideal properties for blood brain penetration which is supported in preclinical studies. This agent shows promising activity in preclinical orthotopic PDX models of GBM and is an ideal first-in-class agent to investigate. In this study, we propose the first-ever experience with this agent in patients with recurrent GBM.

2.4 Correlative Studies Background

Pharmacokinetic Assessment

Pharmacokinetics:

In the existing experience in the single-arm phase I study of PT2385 in patients with renal cell carcinoma (RCC), pharmacokinetic data suggests that a small subset of patients may rapidly metabolize PT2385 into its inactive metabolite, thus limiting exposure to drug. To

further explore this variability, pharmacokinetic data will be assessed. Plasma concentrations of PT2385 and PT2639 will be determined by validated liquid chromatography/mass spectrometry methods. All PK studies and analyses will be funded by Peloton Therapeutics and contracted by Peloton Therapeutics through an external vendor which has been feasible in the ongoing phase 1 study in RCC. All PK studies and analyses will be performed by Peloton Therapeutics.

Pharmacogenomic Assessment:

PT2385 is metabolized by the polymorphic CYP2C19 (PMID 10971203) and CYP3A4 (PMID 16509759), suggesting the potential for CYP2C19 and CYP3A4 polymorphisms to influence the metabolism of PT2385 and potentially contribute to patient-to-patient variability in drug metabolism. Data from the phase 1 study in ccRCC are being gathered to explore potential explanations but a genomic target and validated assay do not currently exist. The primary objective of the study proposed is to determine the radiographic response rate and the study is designed to achieve this objective. Whole blood samples will be collected for sequencing of genes that may be involved in regulating PT2385 metabolism. Samples will be stored by Peloton Therapeutics for future pharmacogenomics analysis.

Pharmacodynamic Assessment

Pharmacodynamic markers to be assessed may include, but are not limited to, levels of erythropoietin (EPO) and vascular endothelial growth factors (e.g. VEGF, soluble VEGF). These markers have demonstrated the most promise based on data from the phase I study in ccRCC. Plasma concentrations of EPO and VEGF will be determined by commercially available ELISA contracted through an external vendor and funded by Peloton Therapeutics. This process has been feasible in the phase 1 study in ccRCC. All PD studies and analyses will be performed by Peloton Therapeutics.

Hypoxia Imaging

Patient selection is a critical component of the therapeutic development of targeted agents. While hypoxia is central to the pathogenesis of GBM, biologic response to agents that target hypoxia pathways may vary based on the degree of hypoxia present, the reliance on hypoxic pathways, and other factors. As such, critical to the development of the proposed agent is the exploration of imaging and other methods to inform patient selection. While several modalities hold promise in imaging hypoxia, no clinically available gold standard currently exists. Two innovative hypoxia and pH-weighted MR-based imaging sequences have been recently developed by a collaborator through the ABTC ([name]/UCLA). These sequences and associated endpoints are an exploratory component of this study. The sequences will not be used to evaluate radiographic response or progression (i.e. PFS) and are not designed as companion or integral biomarkers in this study. Importantly, tumor hypoxia and acidity are hypothesized to be potential drivers of HIF2a expression and may not change as a result of HIF2a inhibition; however, pre-treatment levels of hypoxia and acidity may predict patients that respond from inhibition of HIF2a. The proposed advanced imaging will be performed at baseline to explore the degree of hypoxia present at treatment

initiation. The objective for this correlative imaging component of the study is to describe the hypoxia signature of these tumors at baseline and explore possible correlations with clinical outcomes.

Fast pH-weighted Molecular Magnetic Resonance Imaging (MRI) using Amine CEST-EPI: The chemical exchange between amine and amide protons in bulk water has been shown to be pH dependent using an imaging method called chemical exchange saturation transfer (CEST) imaging. In a recently set of published studies by [name] and colleagues, pH-weighted imaging was shown to have high spatial correspondence between regions of tumor acidity, elevated choline on MRS, elevated lactate on MRS, and elevated ^{18}F -FDOPA uptake (Figure 4, Harris et al., 2015; Harris et al., 2016). Results also suggested patients with acidic lesions (**Figure 4D**) were more likely to progress earlier after starting radiochemotherapy (**Figure 4F**), while patients with non-acidic lesions (**Figure 4E**) were more likely to respond favorably to therapy. Further, if tumors became less acidic during treatment they were also more likely to have a favorable PFS (Harris et al., 2015). Together, these results suggest characterization of intratumoral pH may be an important biologic feature that should be quantified in GBM patients, particularly for therapies that focus on manipulating the microenvironment, metabolism, or oxygenation.

[figure not shown]

Figure 4: Amine CEST-EPI Imaging

Fast Hypoxia-Weighted MRI using Multi-Echo Spin-and-Gradient Echo (ME-SAGE)-EPI:

Recently, investigators have demonstrated the ability to estimate simultaneous T2 and T2* maps using multi-echo spin-and-gradient echo planar imaging (ME-SAGE)-EPI. Using a combination of T2, T2* and relative cerebral blood volume (rCBV), Magnetic Resonance (MR) estimates of relative oxygen extraction fraction (rOEF) can be acquired (Hirsch et al., 2014; He et al., 2007; Toth et al., 2013). Pilot results suggest these rOEF maps show measurable changes as a result of radiotherapy (**Figure 5**) (Toth et al., 2013). Thus, we will

acquire rOEF maps prior to HIF2a inhibition in order to explore whether patients with relatively hypoxic tumors respond favorably to PT2385. Using a combined multi-echo CEST-SAGE-EPI acquisition we will simultaneously estimate both pH and rOEF in the current study.

[figure not shown]

Figure 5: Hypoxia Weighted CEST-EPI-MTR Imaging showing (K) post-contrast T1-weighted image of a centrally ringenhancing recurrent GBM, (L) fluid attenuated inversion recovery (FLAIR) image of this lesion with surrounding edema, (M) FDOPA-PET demonstrating central regions of increase dopamine uptake, and (N) hypoxia-weighted CEST-EPI-MTR sequences showing regions of hypoxia extending beyond the centrally enhancing necrotic focus into region of FLAIR abnormality.

3.0 PATIENT ELIGIBILITY CRITERIA

3.1 Patient Sample

Sample Size:

Minimum: 24 patients / Maximum: 35 patients

Accrual Rate:

3-5 patients per month

Gender:

Male and female

Age:

Patients must be at least 18 years of age.

Race:

Minorities will be actively recruited. No exclusion to this study will be based on race or ethnicity.

PLANNED ENROLLMENT REPORT

Racial Categories	Ethnic Categories				Total
	Not Hispanic or Latino		Hispanic or Latino		
	Female	Male	Female	Male	
American Indian/ Alaska Native	0	0	0	0	0
Asian	1	2	0	0	3
Native Hawaiian or Other Pacific Islander	0	0	0	0	0
Black or African American	2	3	0	0	5
White	7	15	2	3	27
More Than One Race	0	0	0	0	0
Total	10	20	2	3	35

3.2 Eligibility Criteria

1. Patients must have histologically confirmed glioblastoma that is progressive or recurrent following radiation therapy and temozolomide according to the Response Assessment in Neuro-Oncology (RANO) criteria with:
 - a) New contrast-enhancing lesion outside of radiation field on decreasing, stable, or increasing doses of corticosteroids.
 - b) Increase by $\geq 25\%$ in the sum of the products of perpendicular diameters between the postradiotherapy scan with the smallest tumor measurement and a scan at least 12 weeks from completion of RT+TMZ, on stable or increasing doses of corticosteroids.

Note: clinical deterioration not attributable to concurrent medication or comorbid conditions is sufficient to declare progression on current treatment but not for entry onto a clinical trial for recurrence.

2. Tumor O(6)-methylguanine-DNA-methyltransferase (MGMT) methylation status must be available. Results of routinely used methods for MGMT methylation testing (e.g. methylation-specific polymerase chain reaction, MSPCR, or quantitative PCR) are acceptable.

3. Patients must have a tumor tissue form indicating availability of archived tissue from a previous surgery for glioblastoma, completed and signed by a pathologist. See Section [9.5.5](#).
4. Patients must have measurable (defined by at least 1 cm x 1 cm) contrast-enhancing disease by MRI imaging within 21 days of starting treatment.
5. Patients must be able to undergo MRI of the brain with gadolinium. Patients must be maintained on a stable or decreasing dose of corticosteroid regimen (no increase for 5 days) prior to this baseline MRI.
6. Patients must be in first recurrence of glioblastoma following radiation therapy and temozolomide.
7. Patients must have recovered from severe toxicity of prior therapy. The following intervals from previous treatments are required to be eligible:
 - 12 weeks from the completion of radiation.
 - 6 weeks from a nitrosourea chemotherapy
 - 3 weeks from a non-nitrosourea chemotherapy
 - 4 weeks from any investigational (not FDA-approved) agents
 - 2 weeks from administration of a non-cytotoxic, FDA-approved agent (e.g., erlotinib, hydroxychloroquine, etc.)
8. Patients must be 18 years of age or older.
9. Patients must have a Karnofsky Performance (KPS) Status \geq 60% (i.e. the patient must be able to care for himself/herself with occasional help from others).
10. Patients must have the following organ and marrow function:

Absolute neutrophil count	\geq 1,500/mcL
Platelets	\geq 100,000/mcL
Hemoglobin	\geq 9 g/dL
Total bilirubin	\leq institutional upper limit of normal
AST (SGOT)/ALT (SGPT)	\leq 4 \times institutional upper limit of normal
Creatinine	\leq institutional upper limit of normal
OR	
Creatinine clearance	\geq 60 ml/min/1.73m ² for patients with creatinine levels above institutional normal
APTT or PTT	\leq 1.5 x institutional upper limit of normal

11. Patients must be able to provide written informed consent.
12. Women of childbearing potential must have a negative serum pregnancy test prior to study start. Women of childbearing potential and men must agree to use adequate contraception (hormonal or barrier method of birth control; abstinence) prior to study entry, for the duration of study participation, and through 30 days after the last dose of study drug. Should a woman become pregnant or suspect she is pregnant while participating in this study, she should inform her treating physician immediately. Men treated or enrolled on this protocol must also agree to use adequate contraception prior to the study, for the duration of study participation, and through 30 days after the last dose of study drug.
13. Patients must have no concurrent malignancy except curatively treated basal or squamous cell carcinoma of the skin or carcinoma in situ of the cervix, breast, or bladder. Patients with prior malignancies must be disease-free for \geq five years.
14. Patients must be able to swallow tablets.

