4.4 General Concomitant Medication and Supportive Care Guidelines

Prohibited Concomitant Medications During Study

Patients may receive other medications that the investigator deems to be medically necessary, with the specific exception of non-protocol specified chemotherapy, radiotherapy, anti-neoplastic biological therapy or other investigational agents. Patients who require the use of any of the aforementioned treatments for clinical management should be removed from the study.

PT2385 is primarily metabolized by UGT2B17, UGT2B7, UGT2B15, CYP2C19 and CYP3A4. Strong inhibitors of CYP2C19 and CYP3A4 should be avoided in patients receiving PT2385 ([Appendix II](#)).

PT2385 has been shown to induce the enzymes CYP3A4 and CYP2B6 in cultured human hepatocytes. Simcyp PBPK model simulations indicate weak-to-moderate CYP3A4 substrate midazolam DDIs (~50% reduction in midazolam AUC) at the clinically relevant PT2385 doses. Simulations also indicate that PT2385 is a weak CYP2B6 inducer (< 11% AUC reduction for CYP2B6 substrate bupropion at the clinically relevant PT2385 doses). PT2385 is not a potent inhibitor for CYP1A2, CYP2B6, CYP2C8, CYP2C9, CYP2C19, CYP2D6 and CYP3A4 ($IC_{50} > 8.8 \mu\text{g/mL}$). It is unlikely to significantly inhibit these CYPs at the clinically relevant PT2385 concentrations ($C_{\text{max}} \sim 3.14 \mu\text{g/mL}$). A partial list of CYP3A4, CYP2B6, CYP2C9, and CYP2C19 substrates is provided in [Appendix III](#).

Patients taking medications metabolized by CYP3A4 and CYP2B6 should be monitored carefully for decreases in drug effect. Patients taking medications metabolized by CYP2C9 and CYP2C19 should be monitored for potential increases in drug effect.

Corticosteroids

Postoperatively, corticosteroids should be tapered to a stable dose as determined by the clinical status of the patient. The lowest required steroid dose should be maintained throughout the duration of the study in order to eliminate steroid effects as a confounding variable in the interpretation of serial brain imaging studies. Corticosteroid doses can be tapered as clinically indicated if the patient appears to be responding to therapy as judged by serial scans. Corticosteroid dose may, of course, be increased in the event of clinical deterioration or at the discretion of the attending physician. In the event of suspected clinical deterioration, repeat brain imaging is recommended.

Anticonvulsants

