5.3 Use of Hematologic Growth Factors

During the first 28 days of treatment, granulocyte colony stimulating factor (G-CSF) should be administered only for severe or prolonged neutropenia or for neutropenic sepsis. There will be no constraint on the use of growth factors during subsequent treatment; however, prophylactic use is discouraged and adherence to the American Society of Clinical Oncology (ASCO) guidelines is recommended (JCO, 12, 1994: pp 2471-2508). Patients should receive all necessary supportive care, including blood products, transfusions, antibiotics, pain medications, bisphosphonates, and replacement hormonal therapies (insulin, thyroid hormones, estrogen/progesterone).

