8.3 Safety assessments

Safety assessments will consist of monitoring and recording all adverse events and serious adverse events, the regular monitoring of hematology and blood chemistry, pregnancy testing (in women of childbearing potential), regular measurement of vital signs, and the performance of physical/neurological examinations; ECGs and other cardiac monitoring may be performed as necessary.

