APPENDIX III – PARTIAL LIST OF SUBSTRATES OF CYP3A4, CYP2B6, CYP2C9, AND CYP2C19

CYP3A4 Substrates	CYP2B6 Substrates	CYP2C9 Substrates	CYP2C19 Substrates
clarithromycin	artemisinin	ibuprofen	esomeprazole
erythromycin	bupropion	naproxen	lansoprazole
quinidine	efavirenz	tolbutamide	omeprazole
alprazolam	ketamine	glipizide	pantoprazole
diazepam	meperidine	losartan	phenytoin
midazolam	methadone	irbesartan	amitriptyline
cyclosporine	nevirapine	glyburide	carisoprodol
indinavir	propofol	glipizide	citalopram
nelfinavir	selegiline	celecoxib	clopidogrel
ritonavir	sorafenib	fluoxetine	cyclophosphamide
cisapride		rosiglitazone	imipramine
chlorpheniramine		tamoxifen	labetalol
terfenadine		valproic acid	nilutamide
amlodipine		zafirlukast	progesterone
diltiazem			propranolol
nifedipine			teniposide

ABTC # 1602

NCI # ABTC-1602

PI: [name]

atorvastatin lovastatin simvastatin estradiol testosterone carbamazepine codeine fentanyl haloperidol ondansetron			voriconazole
----------------------------------------------------------------------------------------------------------------------------------------------	--	--	--------------

Consult a frequently updated medical reference for possible changes.

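### Section 3.2 item 12 accepts a hormonal method alone as adequate contraception, although section 4.4 predicts CYP3A4 induction and Appendix III lists estradiol as a CYP3A4 substrate

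*Combined protocol and SAP*

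**What the plan says.** Section 3.2 item 12 requires women of childbearing potential, and men, to use adequate contraception before study entry, during participation and until 30 days after the last dose. It accepts "hormonal or barrier method of birth control; abstinence". Any one of these is enough, and hormonal users are not asked for a second method.

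Section 4.4 reports that PT2385 induces CYP3A4 and CYP2B6 in human hepatocytes. For CYP3A4 it cites simulations showing "weak-to-moderate CYP3A4 substrate midazolam DDIs (~50% reduction in midazolam AUC) at the clinically relevant PT2385 doses". Its instruction to sites is: "Patients taking medications metabolized by CYP3A4 and CYP2B6 should be monitored carefully for decreases in drug effect". For two other enzymes the warning runs the other way: "Patients taking medications metabolized by CYP2C9 and CYP2C19 should be monitored for potential increases in drug effect".

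Appendix III gives partial substrate lists. The CYP3A4 column contains the run "simvastatin estradiol testosterone". The CYP2C19 column contains "progesterone".

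Section 3.3 item 8 excludes pregnant women because the effect of PT2385 on a fetus is not known. Under section 4.1, dosing is continuous until progression or unacceptable toxicity.

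**The concern.** Item 12 does not appear to have been adapted to this drug. A woman can meet it with a single method that may depend on a hormone the protocol itself lists as a substrate of an enzyme PT2385 is predicted to induce.

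The general safeguard in section 4.4 is to monitor for reduced effect. That can work for a drug whose waning effect shows clinically and whose dose can be adjusted. It does not work for a contraceptive, because the observable sign of lost effect is the pregnancy. Protection has to come from the contraception rule.

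What is at stake is possible fetal exposure to a drug of unknown fetal risk. No efficacy analysis is involved.

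**Working it through.** There is no design figure to reproduce. The midazolam figure of about 50% is a simulation output whose inputs are not given, so it cannot be rebuilt from the documents. The check sets the sections side by side.

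1. **Is a hormonal method alone enough?** Yes. Item 12 lists alternatives, and no visible text adds a second method for hormonal users.
2. **Does the protocol expect CYP3A4 induction at the doses used?** Yes. Section 4.4 describes it as weak to moderate, on simulation for midazolam, supported by hepatocyte data.
3. **Does the protocol link a relevant hormone to CYP3A4?** Partly. Appendix III lists estradiol in that column. It names no contraceptive product.
4. **Does the protocol say that contraceptive effect falls?** No. Section 4.4 does not mention contraceptives. The step from items 2 and 3 to reduced contraceptive effect is an inference.
5. **Is the direction the same for all hormones?** Not on the documents. Progesterone is listed under CYP2C19, where section 4.4 warns of increased effect. The inference is therefore supported for estrogen-containing methods and left open for progestogen methods.
6. **Can its size be stated?** No. The documents give neither the share of any contraceptive hormone's clearance that runs through CYP3A4 nor a link from exposure to failure.
7. **How does the protocol treat other uncertain interactions?** With caution. Section 3.3 item 9 excludes HIV-positive patients on combination antiretroviral therapy because of potential interactions. Section 4.4 bars enzyme-inducing anti-epileptics while stating that no interaction data exist. An added barrier method is milder than either.

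**Number of women.** The planned enrollment report in section 3.1 gives 10 non-Hispanic and 2 Hispanic women:

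- Full enrollment: 10 + 2 = 12 of 35, and 12/35 = 34%.
- Stop after stage 1, assuming the same proportion: 24 × 12/35 = 8.2, or about 8.

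These are planning figures, since the protocol sets no limit by sex. The number who are of childbearing potential and rely only on a hormonal method is not given and may be zero.

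**The case against.** The strongest reply is that the key link is absent from the documents. The only quantified interaction is simulated and concerns midazolam, no contraceptive is named, and progesterone points the other way. Estradiol may also be listed for another reason, because section 5.3 permits "replacement hormonal therapies (insulin, thyroid hormones, estrogen/progesterone". This stands as a limit on strength. It does not remove the estradiol listing, since the listed metabolic route is the same whatever the hormone is taken for.

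A second reply is that a barrier requirement for every hormonal user goes beyond the hormone-specific evidence, which concerns estradiol only. That is true. The wider rule is still reasonable because the documents do not settle progestogen methods, and adding a barrier while keeping the hormonal method does not reduce protection.

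A third reply is that Appendix IV (the patient handout and wallet card) or the consent form may already warn patients. Their text is not available here, so one cannot say that patients go unwarned. Such a warning would not change the eligibility rule, which would still accept the hormonal method alone.

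A reader might go further in two ways:

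- **Carrying the midazolam figure over.** One might infer that contraceptive exposure falls by about half, or that hormonal contraception fails on PT2385. Neither is supported, because the simulated figure is for midazolam and is applied to no contraceptive hormone.
- **Using the pregnancy-test schedule as a measure of this risk.** Section 8.3 names "pregnancy testing (in women of childbearing potential" as a safety assessment, while the table in section 9.1 schedules the test only at baseline. Test frequency is a separate matter. It says nothing about how well a hormonal method works, and the change proposed here leaves it as it is.

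**Conclusion.** The point holds as a low-priority safety improvement. Item 12 states a rule that gives weaker protection than the protocol's own interaction text would suggest, for a drug with unknown fetal effects.

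The conclusion rests on two assumptions: that the CYP3A4 induction predicted in section 4.4 occurs in patients, and that the estradiol listing is relevant to estrogen-containing contraceptives. Loss of contraceptive effect remains an inference of unknown size. The women affected are an unknown, probably small subset of roughly 12 planned, and possibly none. The primary endpoint, sample size and error rates are untouched.

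**What to change.** Add one sentence to section 3.2 item 12, for example: *A woman of childbearing potential who uses a hormonal method must also use a barrier method throughout the period stated in this item.* Leave barrier methods, abstinence and the rule for men as they are. Check Appendix IV and the consent form, and align them if they do not already say this.

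The change needs no extra visit or test. Its cost is the amendment text and a slightly stricter requirement for a small, unknown number of women.
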